### 3.2.3. Experience in Humans

At the time of writing of Protocol Version 2.0, Phase II of the current study has been completed and all 30 enrolled patients have been treated (15 in Arm A [best supportive care (BSC) + IFX-1] and 15 in Arm B [BSC alone]) for up to 28 days. Relative change (%) from baseline to day 5 in oxygenation index was assessed as the primary endpoint along with additional clinical parameters until day 28. Relative change in the oxygenation index at day 5 showed no differences between treatment groups. However, IFX-1 treatment was associated with a lower 28-day all-cause mortality when compared to the BSC arm, along with trends in disease improvement, as evidenced by fewer patients experiencing renal impairment assessed by eGFR, more patients showing reversal of blood lymphocytopenia and a greater lowering of lactate dehydrogenase concentrations. In IFX-1-treated patients, pulmonary embolisms (PE) reported as serious adverse events (SAEs) were lower compared to the BSC arm. Also, a temporary increase of D-dimer levels, as potential expression of induction of blood clot lysis, was detected in the first days after initiation of IFX-1 treatment.

Over a treatment period of 28 days, patients in the IFX-1 arm received a maximum of 7 doses of 800 mg IFX-1 intravenously (IV) on separate days. At randomization, 18 patients (60%) were intubated, and 12 patients (40%) had other oxygen supply. A higher number of patients with 2 or more comorbidities associated with increased COVID-19 mortality were reported in the IFX-1 treatment arm compared to the BSC arm. Twenty-eight-day all-cause mortality in the IFX-1 treatment arm was 13% (2 out of 15) versus 27% (4 out of 15) in the BSC arm. In the BSC arm, 4 patients died of COVID-19-induced multi-organ failure, and 3 of them had PE reported as SAEs. In the IFX-1 arm, one patient died after an acute ventilator tube complication (leakage) and one patient with a history of severe chronic obstructive pulmonary disease died of pulmonary failure. Serious AE rates were comparable between groups, but the rate of PE reported as SAEs was substantially lower in the IFX-1 treatment group. Upon review of the safety data, the independent data safety monitoring board has recommended continuation of the trial into Phase III.

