#### **10.1.3.1. Efficacy Analyses**

The relative change (%) from baseline (day 1 prior to study drug administration at  $\pm 1$ h of randomization) in oxygenation index ( $\text{PaO}_2 / \text{FiO}_2$ ) in supine position at day 3, 5, 9, and 15 was to be analyzed with a linear repeated measures model with post-baseline time points as outcome variable and baseline value as explanatory variable. Deceased patients were to be included in the model with an outcome of 0 after death. Patients discharged from the ICU whose oxygenation index was no longer be assessed were to be analyzed by last observation carried forward. Treatment arm, time point, the interaction between treatment arm and time point, the interaction between baseline and time point, age, sex, and intubation status at baseline was to be included as further explanatory variables. The model was to use an unstructured covariance matrix and make use of the Kenward-Roger degrees of freedom approximation. Least square mean differences between treatment arms and their 95% confidence interval was to be calculated and displayed for each time point separately (day 3, 5, 9, and 15), with the evaluation at day 5 reflecting the primary endpoint. If oxygenation index was to be used as the primary endpoint for a Phase III part of the study, data from both study parts were planned to be analyzed in one combined model as specified above with study part as a random effect.

Early response, late response and reaching ICU discharge alive were to be analyzed as three separate time-to-event variables. Withdrawing early from the study would have led to the patient

being right-censored at the date of withdrawal provided that the reason was not an outcome of interest for the time-to-event endpoint. In order to adequately account for competing outcomes as well as potential right-censoring due to varying follow-up times, these outcomes were to be non-parametrically analyzed using Aalen-Johansen-type estimation based on a competing risks model with two absorbing states (event 1: all-cause death; event 2: early response/late response/ICU discharge respectively). The Aalen Johansen estimator estimates the expected relative number of patients (cumulative incidence function [CIF]) of the event at hand. Treatment effects were to be derived in terms of the absolute differences between the treatment arm-specific estimators evaluated at day 7:

$$[\text{Effect}]_{-(Y;7)} = \text{CIF}_Y^A(7) - \text{CIF}_Y^B(7)$$

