#### 10.2.3.2. Secondary Efficacy Analyses

The secondary efficacy analyses will be performed based on the FAS.

The first secondary efficacy endpoint will only be addressed with statistical hypothesis tests if the primary endpoint is statistically significant using the full overall 2.5% one-sided alpha. If the first secondary endpoint is also statistically significant, the full 2.5% one-sided alpha will be passed to the 4 remaining secondary endpoints. Multiplicity in the secondary endpoints will be addressed with the fallback method. 60-day mortality will be analyzed similar to 28-day mortality and the other secondary endpoints will be evaluated using a logistic regression model with the explanatory variables randomized treatment arm (Arm B versus Arm A) and age for:

1. 60-day all-cause mortality
2. Proportion of patients with an improvement in the provided 8-point ordinal scale at day 15 (at least one score point lower than at randomization)
3. Proportion of patients with an improvement in the provided 8-point ordinal scale at day 28 (at least one score point lower than at randomization)
4. Proportion of patients developing acute kidney failure ( $eGFR < 15 \text{ mL/min}/1.73\text{m}^2$ ) during ICU stay and at day 28
5. Proportion of patients free of any renal replacement therapy within 28 days upon randomization
- 6.

The ordering of the secondary endpoints 2 to 5 for hypothesis testing will be as in above mentioned list. The full 2.5% one-sided alpha for the fallback method will be attributed to the 4 secondary endpoints in the following way 2%, 0.2%, 0.2%, and 0.1%. If the preceding hypothesis test is not significant, subsequent tests will be performed at the aforementioned alpha level. If tests are significant, the alpha is added to the subsequent hypothesis test (e.g., if the primary hypothesis test is significant and secondary endpoints 1-4 are all significant, the fifth secondary endpoint will be tested at an alpha of 2.5%; if the fourth secondary endpoint is not significant, the fifth secondary endpoint will be tested at an alpha of 0.1%).

The primary endpoint as well as all secondary endpoints will also be evaluated as censored time to event variables by Kaplan-Meier type methods. Kaplan-Meier analyses will be performed comparing the two treatment arms overall and within the following stratifications:

- Stratification by site
- Stratification by country

- Stratification by sex
- Stratification by age
- Stratification by comorbidities

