- Stratification by standard or care.

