#### **10.2.3.3. Other Efficacy Analyses**

##### *Time to First Extubation*

Time to first extubation will be analyzed as a censored time to event variable. Withdrawing early from the study will lead to the patient being right-censored at the date of withdrawal provided that the reason is not an outcome of interest (extubation or death). In order to adequately account for competing outcomes as well as potential right-censoring due to varying follow-up times, the outcome will be non-parametrically analyzed using Aalen-Johansen-type estimation based on a competing risks model with two absorbing states (event 1: all-cause death; event 2: extubation). Adjustment for age will be realized by regression modeling accounting for competing risks.

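### Supplementary Kaplan-Meier analyses are planned for the non-fatal secondary endpoints 2–5, where death is a competing event; the protocol uses Aalen-Johansen for extubation

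*Combined protocol and SAP*

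**What the plan says.** The main analysis of endpoints 2–5 is not Kaplan-Meier. Section 10.2.3.2 (Version 4.0) states that "the other secondary endpoints will be evaluated using a logistic regression model with the explanatory variables randomized treatment arm (Arm B versus Arm A) and" (the second variable is age). It then adds a second layer: "The primary endpoint as well as all secondary endpoints will also be evaluated as censored time to event variables by Kaplan-Meier type methods". The Phase III statistical methods in the synopsis carry the same sentence. The scope is wide: "Kaplan-Meier analyses will be performed comparing the two treatment arms overall and within the following stratifications", followed by site, country, sex, age, comorbidities and finally "Stratification by standard or care" (evidently standard of care). Neither place names a competing-risk method or a rule for deaths.

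Section 10.2.3.3, which follows directly, handles time to first extubation differently. It makes all-cause death an absorbing state alongside extubation and uses an Aalen-Johansen estimator, giving as its reason "In order to adequately account for competing outcomes as well as potential right-censoring due to varying follow-up times". Section 10.1.3.1 took the same approach in Phase II for early response, late response and ICU discharge, which were to be "non-parametrically analyzed using Aalen-Johansen-type estimation based on a competing risks model with two absorbing states".

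**The concern.** Kaplan-Meier treats a censored patient as someone who could still have the event later. A patient who has died cannot improve on the ordinal scale, develop kidney failure or start renal replacement therapy (RRT). With deaths censored, one minus Kaplan-Meier (1−KM) estimates what would happen if nobody died first, not the share of patients who have the event. It lies above that share, and the gap grows with mortality. A drug that lowers mortality therefore makes the gap unequal between arms. The same applies between strata whose mortality differs, such as age or comorbidity groups.

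At stake is the reading of supplementary curves. Taken as percentages they would be too high in both arms, by different amounts, and would not match the proportions behind the logistic analysis of the same endpoints. The primary endpoint, the type I error and the alpha-controlled tests do not depend on them.

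**Working it through.** **The plan's own figure.** The mortality rates used here, 30% on placebo and 15% on IFX-1 at day 28, come from Section 10.2.1, which states 90% power with 180 per arm and one-sided 2.5%. A two-proportion calculation gives 91.0% with continuity correction and 92.9% without. The 90% is not in dispute; it only identifies the source of the rates.

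**Inputs.**
- Death: cumulative hazard Hd = −ln(1 − mortality), so −ln(0.70) = 0.357 on placebo and −ln(0.85) = 0.163 on IFX-1. For day 15, multiply by 15/28.
- Non-fatal event: cumulative hazard H = days × daily hazard. The documents give no rates for endpoints 2–5, so these are assumptions, shown over a range.
- All hazards are constant over time, and death risk is the same before and after the event.

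**Formulas.**
- Deaths censored: 1−KM = 1 − exp(−H)
- Share actually having the event (cumulative incidence): H/(H + Hd) × [1 − exp(−(H + Hd))]

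**Improvement, 0.03 per day in both arms, day 28.** H = 28 × 0.03 = 0.84.
- 1−KM = 1 − exp(−0.84) = 56.8% in both arms.
- Placebo: 0.84/1.197 × [1 − exp(−1.197)] = 49.0%
- IFX-1: 0.84/1.003 × [1 − exp(−1.003)] = 53.0%

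| Scenario (same event hazard in both arms) | 1−KM, both arms | True, placebo | True, IFX-1 | Excess in points (placebo / IFX-1) | Excess over the range |
|---|---|---|---|---|---|
| Improvement, day 28, 0.03/day | 56.8% | 49.0% | 53.0% | 7.8 / 3.8 | 3.7–9.4 / 1.8–4.5 for 0.01–0.05/day |
| Improvement, day 15, 0.03/day | 36.2% | 33.2% | 34.8% | 3.0 / 1.4 | 1.2–4.2 / 0.6–2.0 for 0.01–0.05/day |
| RRT or kidney failure, H = 0.3 | 25.9% | 22.0% | 24.0% | 3.9 / 1.9 | 1.5–6.5 / 0.7–3.1 for H = 0.1–0.6 |

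The improvement rows describe first improvement, not the day-15 or day-28 state tested as endpoints 2 and 3.

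**Phase II mortality instead.** Section 3.2.3 reports: "Twenty-eight-day all-cause mortality in the IFX-1 treatment arm was 13% (2 out of 15) versus 27% (4 out of 15) in the BSC arm". At 0.03 per day the true figures are then 49.9% (comparator) and 53.5% (IFX-1) against 56.8%, an excess of 6.9 and 3.4 points.

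**The other direction.** Let the true share with the event be c in both arms, and let d = 30% or 15% die without it. Then 1−KM = 1 − (1 − c − d)^(c/(c + d)). For c = 15%, 30% and 50% it reads 18.1% vs 16.3%, 36.8% vs 32.9% and 63.4% vs 55.4% (placebo vs IFX-1). Equal arms appear to differ by about 2 to 8 points.

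**Coding of deaths.** In a simulation at 0.03 per day with 400,000 patients per arm, censoring deaths gives 1−KM of 56.9% and 57.0%. Keeping deaths event-free to day 28, with no other earlier censoring, gives 49.0% and 53.2%, equal to the observed proportions.

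**The case against.** The strongest reply is that the plan never says deaths are censored. Section 10.2.3 calls itself a summary and leaves exact definitions to a SAP finalized before unblinding; no Phase III SAP text is in the documents. Section 10.2.3.3 also calls extubation a censored time-to-event variable and then treats death as an absorbing state, so that phrase need not imply censoring at death. On the ordinal scale (Appendix 7) death scores 8, which makes a dead patient a known non-improver. This stands to the extent that the bias is conditional on coding. It does not remove the point: Sections 10.2.3.2 and 10.2.3.3 name different methods for the same kind of outcome, without a reason.

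A second reply is that death-censored Kaplan-Meier validly compares cause-specific hazards, and the protocol nowhere promises to read the curves as percentages. That is correct, but such curves are easily read that way.

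Third, the sizes are soft.
- If the death hazard after RRT is 2 to 5 times that before it (an assumption), with total mortality held at 30% and 15%, the excess at H = 0.3 falls from 3.9/1.9 to between 3.5/1.7 and 2.9/1.3 points.
- The arm order can reverse. With the RRT hazard 5% lower on IFX-1 (0.285 vs 0.3), 1−KM reads 25.9% placebo vs 24.8% IFX-1, while the true shares are 22.0% vs 23.0%. At a 10% lower hazard the reversal is gone (22.0% vs 21.9%). It is a selected illustration.
- The difference in bias between arms, about 4 points for improvement and 2 for RRT, is below one standard error of the arm difference at 180 per arm (about 5.3 and 4.4 points).
- By site, 360 patients over about 60 sites is 6 per site, or about 3 per arm, where the bias could not be seen.

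**Conclusion.** The point holds and is minor. The plan names Kaplan-Meier for endpoints 2–5, overall and in six sets of strata, with no provision for death, while using a competing-risk estimator for extubation. If deaths are censored, the curves overstate incidence in both arms and roughly twice as much on placebo: 3.7–9.4 versus 1.8–4.5 points for first improvement by day 28, and 1.5–6.5 versus 0.7–3.1 points for a renal event. These sizes rest on the planned mortality, constant hazards and assumed event rates. If deaths stay event-free to day 28 and there is no other earlier censoring, the error is zero. Only supplementary description is affected.

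**What to change.** Restrict the Kaplan-Meier sentence in Section 10.2.3.2 to 28- and 60-day mortality, and align the same sentence in the synopsis. For any time-to-event display of endpoints 2–5, specify Aalen-Johansen cumulative incidence with death as the competing event, overall and in each stratum, as Section 10.2.3.3 does for extubation. Label the ordinal display as time to first improvement. As a minor addition, the SAP should state how death without a renal event is coded in endpoints 4 and 5 and how patients on RRT are classified in endpoint 4, and should show deaths and renal events separately by arm. No endpoint needs redefining.

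The cost is wording in two places and in the SAP. The data are already collected under Sections 8.2.2.1 to 8.2.2.3 (organ support, ordinal scale, survival status). No extra patients, visits or alpha are needed.

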#### **10.2.3.3. Other Efficacy Analyses**

##### *Time to First Extubation*

Time to first extubation will be analyzed as a censored time to event variable. Withdrawing early from the study will lead to the patient being right-censored at the date of withdrawal provided that the reason is not an outcome of interest (extubation or death). In order to adequately account for competing outcomes as well as potential right-censoring due to varying follow-up times, the outcome will be non-parametrically analyzed using Aalen-Johansen-type estimation based on a competing risks model with two absorbing states (event 1: all-cause death; event 2: extubation). Adjustment for age will be realized by regression modeling accounting for competing risks.

##### *Patients Alive and Free of Respiratory Failure*

Patients achieving 8-point ordinal scale score 3 or below (patients alive and free of respiratory failure) at day 15 and day 28 are defined as alive and free of respiratory failure at the respective study day. The corresponding endpoint will be analyzed using logistic regression with explanatory variables age and treatment group.

##### *Glasgow Outcome Scale*

Glasgow Outcome Scale assessed at study day 60 will be analyzed via ordinal logistic regression with explanatory variables treatment arm (Arm B versus Arm A) and age.

##### *Quality of Life*

Quality of life will be assessed by EQ-5D at study day 60. The visual analogue scale as well as an index value based on the 5 health states (cross-walk index value using the United States value set) will be analyzed by an ANCOVA model with explanatory variables treatment arm (Arm B versus Arm A), age, and sex (male versus female).

#### **10.2.3.4. Safety Analyses**

Safety analyses will be performed based on the SAF.

The occurrence of TEAEs will be compared between treatment arms. TEAEs will be analyzed according to the number and percentage of patients who had a TEAE, as well as the number of TEAEs in total. Additionally, the number and percentage of patients with TEAEs will be further grouped by severity and causal relationship. The number and percentage of patients with serious

TEAEs and AESIs and the number of serious TEAEs and AESIs will be analyzed. Where TEAEs are grouped by severity or relationship, the maximum severity/relationship per patient and class of TEAE will be considered.

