### Number of Patients:

**Phase II:** 30 patients (15 arm A+ 15 arm B)

**Phase III:** Total of 180 patients (approximately 90 per arm) in Stage 1 and 180 patients (approximately 90 per arm) in Stage 2 are planned. The assumed rate for randomization of additional patients, i.e. patients randomized in error (screening failures) and patients for whom consent is withdrawn within 48 hours after randomization, is 10%. The planned maximum number of patients in the study is 400, 200 patients per treatment arm. The sample size ensures 90% power to show superiority of IFX-1 for the primary endpoint of 28-day all-cause mortality. Sample size calculations were based on the assumption that IFX-1 can reduce a 30% mortality under SOC by 50% to a mortality of 15% and that at least 360 patients are evaluable for the primary endpoint for the final analysis.

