### 10.2. Phase III

#### 10.2.1. Sample Size Determination

A total of 180 patients (90 per arm) are planned to be randomized in Stage 1 and up to 180 patients (90 per arm) in Stage 2. For patients randomized in error (screening failures) and patients for whom consent is withdrawn within 48 hours after randomization, additional patients will be randomized. This results in 90% overall power to show efficacy in the final efficacy analysis. The power calculation is based on an overall 2.5% one-sided alpha and an assumed 30% 28-day mortality under Placebo and 15% 28-day mortality under IFX-1 treatment.

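### Phase III safety is compared only as crude percentages and counts; for later non-fatal events a survival difference alone would shift these, and no rate per time at risk is planned

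*Combined protocol and SAP*

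**What the plan says.** All references are to protocol Version 4.0, Phase III.

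- **Safety measures.** Section 10.2.3.4 compares the arms on the safety analysis set (SAF): "TEAEs will be analyzed according to the number and percentage of patients who had a TEAE", together with the total count of TEAEs. For the serious and special-interest categories the measure is the number and percentage of patients with serious "TEAEs and AESIs and the number of serious TEAEs and AESIs will be analyzed". TEAEs are also grouped by maximum severity and by causal relationship. No person-time denominator or time-to-event analysis of safety is named.
- **Mortality assumption.** Section 10.2.1 plans on an "assumed 30% 28-day mortality under Placebo and 15% 28-day mortality under IFX-1 treatment".
- **Collection window.** Sections 9.1 and 9.1.1 collect adverse events until 30 days after the last administration. Section 7.2.1.2 gives doses on days 1, 2, 4, 8, 15 and 22 only while the patient is in hospital. Collection therefore ends at death, or at a time that depends on the length of the hospital stay.
- **Event definitions.** Section 9.6 lists infections other than COVID-19 as an AESI. Section 9.3 has the primary cause of death recorded as an adverse event and on the SAE form.
- **Elsewhere in the plan.** Time to first extubation (Section 10.2.3.3) uses a competing-risks estimate with death as an absorbing state, "In order to adequately account for competing outcomes". Section 10.2.3.2 adds Kaplan-Meier analyses of all secondary endpoints, and Section 4.2.2.2 lists TEAE frequency among those endpoints.

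**The concern.** A crude percentage depends on the event rate and on how long patients are observed. Here the length of observation is expected to differ by arm, because the trial is built on a halving of mortality and death ends the time at risk. A non-fatal event that accrues through an ICU stay can then differ in percentage and in count with no difference in rate.

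Infection is the category where this matters most. It is a named AESI, it accrues over weeks, and it is an obvious question for an agent that blocks an inflammatory mediator. If the drug saves lives as assumed, a reader of Section 10.2.3.4 tables could not tell an effect on infection from the consequence of longer survival. The shift follows from the mortality difference, so a larger sample would not remove it.

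**Working it through.** The plan states no safety figure to reproduce, so the check asks what Section 10.2.3.4 would show if the drug had no effect on event rates.

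**Inputs.** From Section 10.2.1: 28-day mortality 15% (IFX-1) and 30% (placebo), and 180 patients per arm. Assumed, not in the documents: a constant death hazard in each arm, the same constant non-fatal event hazard λ in both arms (0.01, 0.02 or 0.03 per day), and independence of the two.

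**Step 1: death hazards.** μ = −ln(1 − mortality)/28
- IFX-1: −ln(0.85)/28 = 0.005804 per day
- Placebo: −ln(0.70)/28 = 0.012738 per day

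**Step 2: mean patient-days to day 28.** (1 − exp(−28μ))/μ
- IFX-1: 0.15/0.005804 = 25.8
- Placebo: 0.30/0.012738 = 23.6
- Ratio 1.097, so about +10%

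If deaths cluster early (mean day 7), the means are 28 − 0.15×21 = 24.85 and 28 − 0.30×21 = 21.70, or +15%. If they cluster late (mean day 21), they are 26.95 and 25.90, or +4%. With constant hazards, expected counts of non-fatal events rise by the same +10%.

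**Step 3: percentage with a first non-fatal event by day T.** λ/(λ+μ) × (1 − exp(−(λ+μ)T)). The day-52 columns represent a patient dosed to day 22 (22 + 30 = 52) and extend the same hazards to that day.

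| λ per day | Day 28, IFX-1 v placebo | Difference (SE), points | Day 52, IFX-1 v placebo | Difference, points |
|---|---|---|---|---|
| 0.01 | 22.6% v 20.7% | +1.9 (4.3) | 35.5% v 30.5% | +5.0 |
| 0.02 | 39.9% v 36.7% | +3.2 (5.1) | 57.2% v 50.0% | +7.3 |
| 0.03 | 53.0% v 49.0% | +4.1 (5.3) | 70.8% v 62.6% | +8.2 |

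The shift is about 0.4 to 0.8 standard errors at day 28 and 1.0 to 1.7 at day 52. First events per patient-day at risk equal λ in both arms, so the rate ratio is 1.00 throughout.

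**Step 4: count fatal events as TEAEs, as Section 9.3 implies.** Percentage with any event by day 28 = 1 − exp(−28(λ+μ))
- λ = 0.01: 35.8% v 47.1% (−11.3 points)
- λ = 0.02: 51.4% v 60.0% (−8.6)
- λ = 0.03: 63.3% v 69.8% (−6.5)

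The sign reverses. Near the ceiling the difference disappears: with a non-fatal hazard equivalent to 98% over 28 days, the result is 98.3% v 98.6%.

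**Step 5: early events.** For events confined to the first 3 days with 10% or 50% incidence, the difference is 0.1 or 0.5 points.

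**Step 6: shorter collection on IFX-1.** Placebo is observed to day 28. The IFX-1 window T that gives the same percentage p is T = −ln(1 − p(λ+μ)/λ)/(λ+μ). For λ = 0.02, p = 0.3666 and λ+μ = 0.025804, so T = −ln(1 − 0.4730)/0.025804 = 24.8 days. For λ = 0.01 and 0.03 it is 25.1 and 24.5 days. Collection about 3 days shorter on IFX-1 would therefore cancel the day-28 excess, and a greater shortening would reverse it. Survivors' windows can differ by more than that: a last dose on day 8 ends collection on day 38, against day 52 for a last dose on day 22.

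**The case against.** Five points can be made for the plan.

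- **Fatal events are TEAEs.** A reader might infer that the arm with fewer deaths will look less safe overall. The documents do not support that. Step 4 shows the opposite for any TEAE, and any serious TEAE likewise includes the fatal events. This point stands and limits the concern to non-fatal events.
- **Harm would not be hidden.** A reader might also infer that a drug that raised mortality would have its harm masked. Extra deaths would appear as fatal serious TEAEs and in the severity grouping, all-cause mortality is the primary endpoint, and the IDMC reviews safety every 3 months (Section 5.5). Only a difference in non-fatal events could be obscured.
- **No inconsistency with extubation.** With complete follow-up to a fixed day, the Aalen-Johansen estimate planned for extubation equals the crude percentage. The crude figure is a legitimate absolute risk with death as a competing event, and more infections among patients who live longer are real infections. The percentages are therefore not an error; what is missing is a second measure that separates rate from time at risk.
- **Other text may supply it.** The Kaplan-Meier sentence in Section 10.2.3.2 could be read to cover TEAEs. It sits in the efficacy section, on the full analysis set, and is not carried into Section 10.2.3.4, so its reach is unclear. Section 10.2.3 calls itself a summary and defers detail to a SAP to be finalised before unblinding. The combined document contains no separate SAP text on safety, so the addition may yet be made there.
- **Size.** The day-28 shift is below one standard error, needs the full assumed mortality benefit, and enters no specified safety test or stopping rule. That is fair, and it is why this is an improvement and not a defect in the trial's main conclusion.

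**Conclusion.** The concern holds in a limited form. Section 10.2.3.4 offers only percentages and counts, and under the assumed mortality these mix event rate with time at risk. For later non-fatal TEAEs and AESIs such as infections, equal rates would show as an IFX-1 excess of about 2 to 4 points at day 28 (relative risk 1.08 to 1.09). With a window to day 52 the excess would be about 5 to 8 points. It would shrink or reverse if earlier discharge shortened collection on IFX-1.

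These sizes rest on the planned mortality difference being real, and on constant, independent hazards of 0.01 to 0.03 per day, which the documents do not give. If patients kept alive by the drug are also more prone to infection, the rates themselves would differ between arms, so a rate does not remove every effect of survival. The finding does not extend to any TEAE, any serious TEAE or first-infusion reactions.

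**What to change.** In Section 10.2.3.4, or in the SAP before unblinding:

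1. Keep the planned percentages and counts as descriptive.
2. For non-fatal TEAEs, non-fatal serious TEAEs and each AESI class, add events and first events per 100 patient-days at risk on the SAF. Time at risk runs from first dose to death, withdrawal or end of collection; for first events it also stops at the event.
3. For the same categories, compare time to first event with a cause-specific Cox model that censors at death.
4. Show fatal and non-fatal TEAEs separately, so that the opposing movements in Steps 3 and 4 can be seen.
5. State whether the Kaplan-Meier sentence in Section 10.2.3.2 is meant to cover TEAEs and, if so, on which analysis set.
6. Define the end of collection for both arms. The opening of Section 9 collects events to end of treatment, while Sections 9.1 and 9.1.1 run to 30 days after the last IFX-1 administration, a date that placebo patients do not have. These passages must be reconciled before patient-days can be counted.

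The cost is a few extra tables from dates the protocol already collects (event start and stop, dosing, death, withdrawal). The downside is that readers have two measures to read together.
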